5.4 Statistical Method

5.4.1 Subject Disposition

The number and percentage of subjects will be presented for enrolled population, safety population, PK population and evaluable population.

Subject disposition information and reasons for discontinuation (as reported on eCRF) will be summarized per treatment groups and overall for all enrolled subjects. A listing will be presented for data relevant to subject disposition.

5.4.2 Demographic and Baseline Characteristics

Demographic Characteristics

Demographic characteristics will be summarized per treatment groups and overall in the safety population. Demographic characteristics include age, age groups (<65, ≥65), gender, race, ethnicity, ECOG performance status, height, weight.

Baseline Disease Characteristics

For current cancer history, including cancer type, cancer stage at diagnosis and study entry, summary statistics will be presented for safety population by each treatment group and overall. Current cancer types will be categorized into Adrenal Cortical Carcinoma, Lung Cancer, Colorectal Cancer, Ovarian Cancer, Breast Cancer, Intrahepatic Cholangiocarcinoma, Urothelial Carcinoma and other. In addition, the 95% confidence interval for percent of subjects in each cancer type will be estimated from binomial distribution.

Prior Cancer Therapies

Prior cancer therapies for current cancers are composed of prior surgery, systemic therapy and radiotherapy. Descriptive summary statistics on prior cancer therapies, including any prior cancer therapies (surgery/radiotherapy/systemic therapy) and regimen number of systemic therapy will be presented for safety population by each treatment group and overall. Individual subject listings for prior surgery, systemic therapy and radiotherapy will also be presented.

Prior and Concomitant Medications

Prior medication is defined as any medication taken within 30 days of the stating of ARQ 087 and ending prior to the start of study treatment.

Concomitant medication is defined as any medication besides the study treatment that was administered to a subject coinciding with the study assessment period.

Descriptive summary statistics on the prior and concomitant medications will be presented for safety populations by each treatment group and overall in ATC class and preferred term.

In addition, the related listings will be presented.

5.4.3 Pharmacokinetic Analysis

Pharmacokinetic analysis of ARQ 087 plasma concentrations will be performed separately from this analysis plan, a separate PK report will be generated.

PK parameters of ARQ 087 (AUC_{0-t}, AUC_{0-inf}, C_{max} and t_{1/2}) may be summarized using mean, standard deviation, median, coefficient of variation, minimum and maximum for the full PK assessments. For single PK time point assessments, only plasma concentrations of ARQ 087 will be presented.

If appropriate, logistic regression will be performed on tumor response (CR, PR and SD combined vs. PD) with each PK parameter (C_{max} and AUC_{0-t} at cycle 1 day 22/23) and assigned dose level as independent variable for safety and evaluable population; the logarithmic transformation will be applied to AUC and C_{max} when conducting the logistic regression. The odds ratio and 95% confidence interval will be estimated for each covariate from logistic regression.

Separate sample collection listings for PK full assessment and single assessment of plasma by subject will also be provided for safety population.

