Preliminary PK results reported in subjects enrolled in Cohorts 1-3, have shown that ARQ 087 has a long half-life (~ 1 week) and accumulates with continuous dosing in human subjects (~4 to 14 fold across all cohorts, 4 to 8 fold in cohorts dosed at  $\geq 100$  mg qd). Additionally, preliminary PK results showed that Day 22 exposure (AUC and  $C_{max}$ ) remained essentially the same when increasing the dose from 250 to 425 mg qd, suggesting that drug exposure has reached a plateau at dose levels above 250 mg qd. The ArQule Medical Monitor and Investigator(s) will review all significant ARQ 087-related toxicities and PK data to determine if the dose escalation schedule requires modification. Intermediate doses or different drug administration schedules (e.g., 2 weeks on/1 week off) may be investigated after agreement between ArQule's Medical Monitor and the Investigator(s).

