## 6.6 Pharmacodynamic Assessments

The goal of the proposed biomarker study is to evaluate the tumoral and serum- or plasma-based pharmacodynamic response in subjects treated with ARQ 087.

Information on tumor FGFR protein expression, gene copy number and mRNA amplification, and/or mutational/gene re-arrangement (fusion, translocation) status is required for this study. If these are not known, tumor biopsy should be done to assess these parameters prior to the first dose of ARQ 087. All baseline samples (archival or newly acquired) will be evaluated by immunohistochemistry (IHC), FISH (gene copy number), ISH or qNPA (mRNA amplification), and/or DNA sequencing (mutational/gene re-arrangement [fusion, translocation] status assessment).

Pathology specimens (pre- and post-treatment tumor biopsies) will be evaluated for changes in total FGFR1, total FGFR2, pFGFR, pFRS2 $\alpha$ , and/or pERK status by either IHC, mesoscale, or immunoprecipitation/Western blot analysis. A post-treatment tumor biopsy should be collected between Cycle 1 Day 22 and Cycle 2 Day 1 at least 1 hour post-dose. In subjects who have been on treatment  $\geq 8$  weeks and with the subject's agreement, additional post-treatment biopsies may be collected.

Blood samples (pre-dose) will be collected during Treatment Period 1 on Day 1, Day 2, Day 3, and Day 4 (Cohorts 1-4), and during Treatment Period 2 Cycle 1 (Cohort 5 and all subsequent Dose Escalation cohorts) on Day 1, Day 8, Day 15, and Day 22, and on Day 1 of Cycles 2-5 for evaluations of pharmacodynamic changes of factors including phosphate, glucose, FGF 19, 21, and/or 23 utilizing standard blood chemistry methodologies and ELISA-based assays.

For subjects enrolled in the Expanded Cohort, blood samples for evaluations of pharmacodynamic changes of FGF 19, 21, and 23 will be collected on Day 1 of the first six cycles.

Samples for pharmacokinetic and pharmacodynamic assessments will be labeled by personnel from the institution with subjects' study ID; subjects' identity will not be made known to employees from the Sponsor, additional collaborators, or other investigators. Samples will only be used for the purposes of the protocol and will only be used by ArQule's personnel or by an external laboratory chosen by ArQule to outsource the analyses according to internal guidelines. Samples will be kept until all protocol-related analyses are completed, for a period not exceeding 10 years or as required by local law.

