2.2 Overview of Study Design

2.2.1 Dose Schemes

This is an open-label phase 1/2 study of ARQ 087 in adult subjects with advanced solid tumors that has been enrolled in two parts. Part 1 enrolled subjects with solid tumors and Part 2 only enrolled subjects with FGFR genetic alterations, including intrahepatic cholangiocarcinoma with FGFR2 gene fusion. Treatment will be initiated at a dose level of 25 mg/QOD (every other day).

Part 1: Dose Escalation Cohorts

In cohorts 1-4, treatment consisted of two treatment periods: Treatment Period 1 (single dose administration for 72-hour PK assessment) and Treatment Period 2 (continuous dosing that will cease at the subject's discontinuation from the study).

Given the long half-life (about 1 week) of ARQ 087 in human subjects and the length of time (about 35 days) to reach steady state it was determined that it was reasonable to eliminate the single dose phase. Hence, starting with cohort 5, treatment consisted of a single treatment period of continuous dosing that ceased at the subject's discontinuation from the study.

The Maximum tolerated dose (MTD) was defined as the dose level at which no more than one subject with a DLT was observed among six subjects. Once the MTD was determined, up to six additional subjects might be treated at this dose level of ARQ 087. If the MTD was not reached, dose escalation would have to proceed with the purpose of determining a RP2D of ARQ 087.

Part 2: Expanded Cohort

Based on the drug safety profile and preliminary food-effect cohort PK data, 300 mg qd under fasting conditions has been defined as the RP2D and is recommended for further evaluation in the expanded cohort. Approximately 50-60 subjects with advanced solid tumors with FGFR genetic alterations, including iCCA with FGFR2 gene fusion planned to be enrolled in expanded cohort. The tumor type eligibility was to be confirmed by the Sponsor's Medical Monitor or designee prior to enrollment. If, at the time of the first restaging (C3D1), in two out of the first five enrolled subjects with the same tumor type, an objective response (significant, $\geq 15\%$, reduction in tumor size) was not achieved, such tumor sub-cohort would have to be closed for further enrollment.

There were 11 dose cohorts (Part 1 and Part 2) as listed below (see Table 1).

Table 1: Dosing Guidelines for ARQ 087

Part/Period	Cohort	Total Daily Dose ^a	Dose per Administration	Number of Subjects
Part 1/Period 1	1 ^a	25 mg	1 cap x 25 mg x qod	3-6 ^b

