5 STATISTICAL METHODS AND DATA ANALYSIS

5.1 Determination of Sample Size

No formal statistical tests of hypotheses will be performed in this study. The exact number of subjects estimated for this study depends on the number of cohorts investigated based on the toxicity encountered. It is expected that approximately 60-120 subjects will be enrolled in this study.

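### The exploratory exposure-response model in SAP 5.4.3 has no term for FGFR status or tumour type, so its dose odds ratio can pick up patient selection

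*SAP*

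**What the plan says.** SAP 5.4.3 (Pharmacokinetic Analysis) states, subject to being appropriate, that "logistic regression will be performed on tumor response (CR, PR and SD combined vs. PD) with each PK parameter". The parameters in question are the log-transformed AUC0-t and Cmax from the Day 22/23 profile. Dose enters through a further phrase: "and assigned dose level as independent variable for safety and evaluable population". On reporting, the section says: "The odds ratio and 95% confidence interval will be estimated for each covariate from logistic regression". No FGFR, tumour-type or cohort term is named.

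On who was enrolled at which dose, SAP 2.2.1 says: "Part 1 enrolled subjects with solid tumors and Part 2 only enrolled subjects with FGFR genetic alterations". Part 2 is the 300 mg Expanded Cohort. Protocol sections 3 and 4.1.1 describe the 400 mg Food-effect Cohort. Its subjects had either a listed tumour with an FGFR1-3 alteration, or adrenocortical carcinoma, cholangiocarcinoma or sarcoma whatever their FGFR status.

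On exposure, the text after Protocol Table 4.1 reports Day 22 results "suggesting that drug exposure has reached a plateau at dose levels above 250 mg qd". Protocol 6.5 provides for PK sampling in up to 10 Expanded Cohort subjects. On the missing covariate, Protocol 6.6 says that tumour FGFR expression, copy number and/or "mutational/gene re-arrangement (fusion, translocation) status is required for this study".

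SAP 5.1 says: "No formal statistical tests of hypotheses will be performed in this study".

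**The concern.** The two selected cohorts sit high in the dose range, and the trial expects selection to matter. Identifying FGFR2-fusion iCCA as a target population is a secondary objective, and FGFR as a predictive biomarker is an exploratory one. Protocol 4.1.1 already describes two FGFR2-fusion iCCA subjects in the Food-effect Cohort with tumour reductions of 34% (PR) and 26% (durable SD). Both count as disease control and both carry a 400 mg dose. A model containing only PK and dose has nowhere to put that advantage except the drug terms.

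What is at stake is how the reported dose odds ratio is read. A value above 1 could reflect who was enrolled at 300 and 400 mg and not what the dose did. The precision of the PK odds ratio is a separate matter, because dose and exposure enter the same model.

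**Working it through.** The plan states no power, effect size or PK variability for this model, so there is no figure to reproduce.

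**Inputs from the documents.** Nine escalation cohorts of 3-6 subjects (25 mg qod to 425 mg), at least 6 subjects at 400 mg, up to 10 Expanded Cohort subjects with PK at 300 mg, and flat exposure above 250 mg.

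**Assumed inputs.** Four subjects per escalation cohort, 15% of them FGFR-altered; all Expanded Cohort subjects altered; all or half of the Food-effect subjects altered; exposure proportional to min(dose, 250 mg); between-subject CV 50% unless stated; dose entered linearly. PK subjects: 9×4 + 6 + 10 = 52.

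**Step 1: is dose tied to selection?** The nine labelled escalation doses sum to 1,550 mg, a mean of 1,550/9 = 172 mg. The selected subjects average (6×400 + 10×300)/16 = 338 mg. It is tied.

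**Step 2: dose term with no drug effect.** The truth is logit P(CR/PR/SD) = a + c×FGFR. The fitted model is logit P = b0 + b1 ln(AUC) + b2 dose. For 30% vs 70% disease control, c = 0.847 + 0.847 = 1.69. For 40% vs 60%, c = 0.405 + 0.405 = 0.81. Two-sided 5% is taken from the 95% interval.

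| Disease control, unselected vs altered | Food-effect subjects altered | Joint-model dose OR per 100 mg | Rejection |
|---|---|---|---|
| 30% vs 70% | all | 1.33-1.34 | 11-12% |
| 30% vs 70% | half | 1.16 | 5.5-7% |
| 40% vs 60% | all | about 1.15 | 6% |

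- At 40% vs 60% with half altered, rejection is 4.8%, so the effect is gone.
- A second layout counts no escalation subject as selected. At 40% vs 80% with 70 subjects and CV 50%, it gives 1.33 and 14%. Across 43-70 subjects and CV 50-80%, it gives 1.29-1.51 and 14-18%.
- With a selection term added, the dose OR is about 1.0 and rejection 3-6%.

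**Step 3: PK term with no drug effect.** In the joint model at 30% vs 70%, the PK odds ratio is 0.98 and rejection is 4%. If dose is dropped and nothing is added, log AUC alone rejects 10-12%, because selection then loads onto exposure.

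**Step 4: precision of the PK term.** If PK alone had 80% power, adding dose gives approximately

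power = Φ((1.960 + 0.842)×√(1−R²) − 1.960),

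where R² is that of ln(AUC) on dose.

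| CV | R² | Power after adding dose |
|---|---|---|
| 30% | 0.68 | 2.802×0.566 − 1.960 = −0.375, about 35% |
| 50% | 0.61 | 2.802×0.625 − 1.960 = −0.210, about 42% |
| 120% | 0.39 | 2.802×0.781 − 1.960 = 0.228, about 59% |

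Simulation at an assumed log-odds slope of 0.8 gives 17% power with dose in the model against 50% with FGFR status instead at CV 30%, and 58% against 80% at CV 120%. At CV 50% the standard error of the log AUC coefficient is 0.44 with dose against 0.31 with FGFR status, a ratio of 0.44/0.31 = 1.42.

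**The case against.** The strongest reply is that this is a conditional, descriptive model in a trial with no formal tests. Type I error and power are not properties that the plan claims, so the rejection rates above serve only as a yardstick for bias and imprecision. That stands.

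Other parts of the reply also stand:

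- The dose bias needs a real difference in disease control between selected and unselected subjects. It is small if the contrast is mild or if many Food-effect subjects came in by tumour type.
- Joint fitting is the natural reading, since an odds ratio is promised for each covariate. But the SAP also writes of an independent variable in the singular, so it should say which is meant.
- A uniform FGFR yes/no variable is not assured in the escalation cohorts. Protocol 6.6 and 6.8 use and/or, and Appendix 1 lists genotyping of unknown tumours only for the Food-effect and Expanded Cohorts.

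A reader might also infer more than the documents support:

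- *That the exposure odds ratio is confounded as planned.* Step 3 shows that it is not while dose is in the model.
- *That the PK term loses half its power.* The loss depends on unstated variability, effect size, sample size and dose coding. The simulated ratio of joint to PK-alone power runs from 0.36 to 0.87 for 43-70 subjects.
- *That the plateau causes the collinearity.* It weakens it: R² is 0.72 without the plateau and 0.61 with it.
- *That the model could mislead RP2D selection.* Protocol 4.1.1 and 4.4 say that the RP2D was set from the safety profile and Food-effect PK data.
- *That 25 mg qod and 25 mg qd share one code.* The SAP does not say how dose level is coded.

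**Conclusion.** The concern holds as a cheap improvement. SAP 5.4.3 omits a selection term in a design where dose and selection are linked. If selected subjects have better disease control, the dose odds ratio is biased upward. With about 52 PK subjects and no drug effect, the bias is about 1.15 to 1.35 per 100 mg, with 6-14% rejection at a nominal 5%. It could be larger with fewer subjects and a stronger contrast, and nil in the mildest case. The PK odds ratio is imprecise but not inflated. All these sizes rest on assumed disease-control rates, FGFR prevalence, PK variability and linear dose. The consequence is a misleading exploratory odds ratio, not an error in dose selection.

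**What to change.** Revise SAP 5.4.3 as follows:

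1. Main model: each log PK parameter plus baseline FGFR alteration status (yes/no).
2. Sensitivity analysis: replace FGFR status with tumour type or a cohort-selection indicator (escalation vs Food-effect/Expanded). This covers Food-effect subjects enrolled regardless of FGFR status and escalation subjects with incomplete genotyping.
3. Fit dose in its own model with the same covariate. State how 25 mg qod and 25 mg qd are coded, for example as average daily dose (25/2 = 12.5 mg for qod).
4. Do not remove dose from the PK model without adding the selection term, because that moves the bias onto PK.

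Items 1 and 4 go together: the FGFR term deals with confounding, and separating dose from PK deals with imprecision. Neither does the other's job.

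The cost is SAP wording, one extra parameter in a small model and possibly some missing FGFR data in Cohorts 1-9. No new assessments are needed.

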#### 5.4.5 Week 4 (Day 23; except Expanded Cohort)

The following assessments will be made during this visit:

- Vital signs (temperature, blood pressure, respiration rate and pulse)
- Blood sample for pharmacokinetics (see Section 6.5)

- Assess AEs
- Record concomitant medications

**Note:** Because the Cycle 1 Day 22 and Day 23 visits are days when the full PK is performed, subjects enrolled in **Cohort 1** (25 mg every other day) Cycle 1 Week 4 visits should be scheduled on the day of ARQ 087 administration and the next consecutive day, when drug is not taken, e.g., Cycle 1 Day 21 and Day 22 or Cycle 1 Day 23 and Day 24.

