## 6.5 Pharmacokinetic Assessments

Pharmacokinetic variables will include  $C_{max}$ , AUC, and half-life. To assess single dose PK, blood samples will be collected for four consecutive days during Treatment Period 1 (Cohorts 1-4), on Day 1 (full assessment), Day 2 (24 hrs post-dose), Day 3 (48 hrs post-dose), and Day 4 (72 hrs post-dose). The washout period between Treatment Period 1, Day 1 and Treatment Period 2, Day 1 Cycle 1 should be at least 72 hours. During Treatment Period 2 (continuous administration of ARQ 087), PK samples will be collected on Day 8, Day 15, Day 22 (full assessment), and Day 23 (24 hrs post-dose on Day 22) of Cycle 1 (see Appendix 3). However, for subjects enrolled in **Cohort 1** (25 mg every other day), Cycle 1 Week 4 visits should be scheduled on the day of ARQ 087 administration and the next consecutive day, when drug is not taken, e.g., Cycle 1 Day 21 and Day 22 or Cycle 1 Day 23 and Day 24. Also, a Cycle 1 Day 1 pre-dose sample should be collected if the Cycle 1 Day 1 visit differs from the Treatment Period 1, Day 4 visit (72 hours).

During continuous administration of ARQ 087 (Cohort 5 and all subsequent cohorts, including ALL subjects enrolled in the Food-effect Cohort, and for up to 10 subjects enrolled in the Expanded Cohort at selected sites), PK samples will be collected on Day 1 (full assessment), Day 2, Day 8 (pre-dose), Day 15 (pre-dose), Day 22 (full assessment), and

Day 23 (pre-dose) of Cycle 1; and on Day 1 and Day 15 of all subsequent cycles (pre-dose), and End of Treatment (see Appendix 3).

The blood sampling date and time and the time of the last dose of ARQ 087 administration prior to PK blood draw should be recorded on the eCRF.

Detailed instructions for collection and shipment of plasma PK samples will be provided in the laboratory manual.

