CxDx	Procedure	Sample	Desired Time
CYCLE 1 DAY 1			
C1D1	Draw blood sample	PK	0 hour (prior to ARQ 087 administration )
C1D1	Draw blood sample	PK	1 ( $\pm 10$ min) hour
C1D1	Draw blood sample	PK	2 ( $\pm 15$ min) hours
C1D1	Draw blood sample	PK	4 ( $\pm 15$ min) hours
C1D1	Draw blood sample	PK	6 ( $\pm 15$ min) hours
C1D1	Draw blood sample	PK	8 ( $\pm 15$ min) hours
C1D1	Draw blood sample	PK	10 ( $\pm 15$ min) hours collect up through Food-effect Cohort then optional for Expanded Cohort
C1D1	Draw blood sample	PK	12 ( $\pm 15$ min) hours collect up through Food-effect Cohort then omit for Expanded Cohort
CYCLE 1 DAY 2			
C1D2	Draw blood sample	PK	24 hours ( $\pm 2$ hrs) (post ARQ 087 administration on Day 1 and prior to ARQ 087 administration on Day 2) collect up through Food-effect Cohort then omit for Expanded Cohort
CYCLE 1 DAY 8			
C1D8	Draw blood sample	PK	Prior to ARQ 087 administration on Day 8
CYCLE 1 DAY 15			
C1D15	Draw blood sample	PK	Prior to ARQ 087 administration on Day 15
CYCLE 1 DAY 22			
C1D22	Draw blood sample	PK	0 hour (prior to ARQ 087 administration)
C1D22	Draw blood sample	PK	1 ( $\pm 10$ min) hour
C1D22	Draw blood sample	PK	2 ( $\pm 15$ min) hours
C1D22	Draw blood sample	PK	4 ( $\pm 15$ min) hours
C1D22	Draw blood sample	PK	6 ( $\pm 15$ min) hours
C1D22	Draw blood sample	PK	8 ( $\pm 15$ min) hours
C1D22	Draw blood sample	PK	10 ( $\pm 15$ min) hours collect up through Food Effect cohort then optional for Expanded cohort
C1D22	Draw blood sample	PK	12 ( $\pm 15$ min) hours collect up through Food-effect Cohort then omit for Expanded Cohort

Blood Collection Schedule for Pharmacokinetic Assessment: Cohorts 5-10 and Food-effect Cohort*			
CxDx	Procedure	Sample	Desired Time
CYCLE 1 DAY 23			
C1D23	Draw blood sample	PK	24 hours ( $\pm 2$ hrs) (post ARQ 087 administration on Day 22 and prior to ARQ 087 administration on Day 23)
CYCLE 2 DAY 1 (and all subsequent cycles)			
CxD1	Draw blood sample	PK	Prior to ARQ 087 administration on Day 1
CYCLE 2 DAY 15 (and all subsequent cycles)			
CxD15	Draw blood sample	PK	Prior to ARQ 087 administration on Day 15
END OF TREATMENT			
EOT	Draw blood sample	PK	

- \* 1. Subjects enrolled in the Food-effect Cohort should take ARQ 087 with their morning meal  
2. PK samples may be collected from up to 10 subjects enrolled in the Expanded Cohort

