1 LIST OF ABBREVIATIONS

AE	Adverse event
ALT	Alanine aminotransferase (SGPT/serum glutamic-pyruvic transaminase)
ANC	Absolute neutrophil count
AST	Aspartate aminotransferase (SGOT/serum glutamic oxaloacetic transaminase)
ATC	Anatomical Therapeutic Chemical Classification
AUC _{0-inf}	Area under the concentration–time curve from hour 0 to infinity
AUC _{0-t}	Area under the concentration–time curve from time 0 up to the last measurable sampling time
BID	Twice daily
C _{max}	Maximum plasma drug concentration
CR	Complete response
CRF	Case report form
CT	Computed tomography
CTCAE	Common terminology criteria for adverse events
CYP 450	Cytochrome P450
DCR	Disease control rate
dL	Deciliter
DLT	Dose limiting toxicity
eCRF	Electronic case report form
ECOG	Eastern Cooperative Oncology Group
ECG	Electrocardiogram
EOT	End of treatment
FGF	Fibroblast growth factor
FGFR	Fibroblast growth factor receptor
iCCA	Intrahepatic cholangiocarcinoma

kg	Kilogram
MedDRA	Medical Dictionary for Regulatory Activities
mg	Milligram
mm	Millimeter
MTD	Maximum tolerated dose
ORR	Overall response rate
PD	Progressive disease
PFS	Progression-free survival
PK	Pharmacokinetic
PR	Partial response
PS	Performance status
QD	Once daily
QOD	Every other day
QTc	Corrected QT interval
RECIST	Response Evaluation Criteria in Solid Tumors
RP2D	Recommended Phase 2 dose
SAE	Serious adverse event
SD	Stable disease
STDM	Study data tabulation model
$t_{1/2}$	Elimination half-life
T_{max}	Time to maximum plasma concentration
TEAE	Treatment emergent adverse event

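### AUC0-t has no fixed window: Day 1 values are not comparable across cohorts, and conflicting sampling passages leave the Expanded Cohort's Day 22/23 window unsettled

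*SAP*

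**What the plan says.** **The analysis.** SAP 5.4.3 states that AUC0-t, among other parameters, may be summarised for the full PK assessments. If appropriate, response (CR, PR and SD combined against PD) is then modelled by logistic regression "with each PK parameter (C_{max} and AUC_{0-t} at cycle 1 day 22/23) and assigned dose level as independent variable", with AUC and Cmax log-transformed. The SAP's abbreviation list defines AUC0-t as running "from time 0 up to the last measurable sampling time". No truncation time is fixed, and there is no rule for a profile without its 24-h sample. SAP 5.2 presents all summary tables by pooled dose group; the Low Dose Group runs from 25 mg QOD to 200 mg QD, which is Cohorts 1 to 6.

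**Day 1 sampling.** Protocol Section 6.5 makes Day 1 a full assessment. Appendix 3 samples Cohorts 1-4 to 72 h after the single dose. It samples Cohorts 5-10 and the Food-effect Cohort to 24 h, through the Day 2 draw. For the Expanded Cohort, the 10-h row reads "hours collect up through Food-effect Cohort then optional for Expanded Cohort", while the 12-h row and the Day 2 (24-h) row both carry "collect up through Food-effect Cohort then omit for Expanded Cohort". Section 6.5 nevertheless lists Day 2 in a schedule that applies "for up to 10 subjects enrolled in the Expanded Cohort at selected sites".

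**Day 22/23 sampling.** Part 1 is sampled to 12 h, plus the 24-h draw on Day 23. For the Expanded Cohort the 10-h sample is again optional and the 12-h sample omitted. The synopsis, Section 6.5 and the Appendix 3 row for Cycle 1 Day 23 all include the 24-h draw; that row has no Expanded Cohort exception. On the other side, Section 5.4.5 is headed "Week 4 (Day 23; except Expanded Cohort)". The Part 2 schedule in Appendix 1 has neither a Day 23 column nor a PK row, and SAP Table 4 repeats it. Section 5.4.4 also excepts this cohort from Day 22 PK, with a pointer to Section 6.5.

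**The concern.** An AUC to the last sample measures exposure only relative to its own window. With a half-life near one week, concentrations change little over a day, so the AUC grows almost in proportion to the time covered. Two profiles with the same true exposure but different last samples will then show quite different AUC0-t values.

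Two uses are affected. In descriptive tables, Day 1 AUC0-t would reflect the sampling design as much as the dose. In the regression, a shortened Day 22 window would be tied to the Expanded Cohort, which is selected for FGFR alterations and may have a different disease control rate for that reason. Falsely low exposure in that cohort could push the exposure-response odds ratio down. It could also make 300 mg look as if it falls below the exposure plateau that protocol Section 4.1.1 reports between 250 and 425 mg qd.

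**Working it through.** The documents give no AUC ratio, so there is no plan figure to reproduce.

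**Inputs**
- Half-life about 1 week, or 168 h (protocol 4.1.1).
- Accumulation of 4 to 8 fold at 100 mg qd or more (protocol 4.4). With R = 1/(1 - exp(-24k)), R = 4 gives k = ln(4/3)/24 and a half-life of about 58 h; R = 8 gives k = ln(8/7)/24 and about 125 h. A half-life range of 60-168 h covers nearly all of this.
- Absorption rate ka is not in the documents. Assumed range: 0.2 to 1.0 per h.

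**Day 1, single dose.** For one compartment with first-order absorption, AUC0-T is proportional to (1 - exp(-kT))/k - (1 - exp(-ka·T))/ka.
- Half-life 168 h, ka 0.2: T = 72 gives 62.29 - 5.00 = 57.29; T = 24 gives 22.85 - 4.96 = 17.89. Ratio 3.20.
- Half-life 60 h, ka 1.0: T = 72 gives 48.88 - 1.00 = 47.88; T = 24 gives 20.96 - 1.00 = 19.96. Ratio 2.40.

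| Day 1 cohort | Last scheduled time | AUC0-t relative to AUC0-24 |
|---|---|---|
| 1-4 | 72 h | 2.4-3.2 |
| 5-10, Food-effect | 24 h | 1 |
| Expanded, Appendix 3 | 8 h | 0.22-0.33 |
| Expanded, Appendix 3, optional draw taken | 10 h | 0.31-0.42 |

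The first two rows meet inside the Low Dose Group: Cohorts 1-4 contribute 72-h values and Cohorts 5-6 contribute 24-h values.

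**Day 22, after 22 daily doses.** A flat profile gives 8/24 = 0.33 and 10/24 = 0.42. Superposition of 22 doses in the same model gives:

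| Expanded Cohort last sample | AUC0-t / AUC0-24 | Shift on the log scale |
|---|---|---|
| 24 h (Day 23 drawn) | 0.99-1.00 | none |
| 10 h | 0.42-0.44 | -0.87 to -0.82 |
| 8 h | 0.33-0.36 | -1.11 to -1.02 |

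The first row uses the linear trapezoid on the scheduled times. It shows that missing 10-h and 12-h samples do not matter once the 24-h sample exists.

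**When truncation can occur.** Section 5.4 or the Part 2 schedule, read alone, gives the Expanded Cohort no Day 22 profile, so the subject would not enter the model. Section 6.5 or Appendix 3, read alone, gives a 24-h profile. A truncated profile arises when a site takes Day 22 from Section 6.5 or Appendix 3 but the Day 23 exclusion from Section 5.4.5, or when the 24-h sample is missed or not measurable.

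**Possible effect on the odds ratio.** These simulations are illustrations only. They assume no true exposure effect, 52 Part 1 and 10 Expanded profiles, disease control of 40% against 75%, and exposure proportional to dose up to 250 mg and flat above. None of these is a document figure.
- Linear dose, no truncation: median odds ratio per log AUC 1.12-1.16, false-positive rate 5-6%.
- Linear dose, all 10 truncated: 0.73-0.75, 10-12%.
- Linear dose, half truncated: 0.91, 6%.
- Linear dose, random mix of 8, 10 and 24 h: 0.86, 5%.
- Truncated, no dose term: 0.93, 5%.
- Truncated, with an Expanded Cohort indicator: 0.99, 4%.

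**The case against.** The strongest reply is that the regression uses only Day 22/23 and that three places in the protocol list the 24-h draw for sampled Expanded Cohort subjects. The Appendix 3 instruction to omit a 24-h sample applies to Day 2, not Day 23. If the sample is drawn, the ratio is essentially 1. This stands. A reader might infer that the Expanded Cohort's exposure covariate is always about one third of the others'. The documents do not support that: for Day 22/23 it is one possible outcome of a conflict, and one third is the 8-h case only. Nor do the Day 1 ratios bear on the regression, which does not use Day 1 AUC.

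The stakes are also limited. The regression is conditional on being appropriate, no hypotheses are formally tested, the PK objective concerns Part 1, and Expanded Cohort PK is optional and limited to about 10 subjects. Because 300 mg is unique to that cohort, a categorical dose term fitted jointly with AUC would absorb a shift common to it. That also stands, but the SAP does not say how dose is coded or whether it enters jointly. A categorical term would not absorb a mix of windows within the cohort.

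Finally, the PK analysis goes to a separate report, which may fix the window. The SAP nevertheless names AUC0-t as the covariate and as a summary parameter, so the definition belongs there. None of these replies removes the Day 1 mixture in the descriptive summaries, although those summaries are themselves optional.

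**Conclusion.** The point holds in two parts of different strength.

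The Day 1 part follows from the schedule as written. AUC0-t covers 72 h, 24 h or, under Appendix 3, 8-10 h according to cohort, and within the Low Dose Group alone the windows would produce a 2.4 to 3.2 fold difference at equal exposure. The conflict between Section 6.5 and Appendix 3 on Day 2 affects only the Expanded Cohort row. The sizes rest on the one-compartment model and the assumed ka.

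The Day 22/23 part is conditional. There is no artefact if the 24-h sample is drawn, and a reduction to 0.33-0.36 or 0.42-0.44 of AUC0-24 if it is not. A reader might go further and conclude that the exposure-response odds ratio will be reversed. That needs most or all Expanded profiles to be truncated, a linear dose term, and a large difference in disease control between cohorts; the documents establish none of these. What they do establish is a covariate without a fixed window and a sampling plan that contradicts itself on the draw that sets the window.

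**What to change.** In SAP 5.4.3, replace AUC0-t with AUCs over stated windows:
- **Day 22/23:** AUC0-24 as the regression covariate and main summary. Exclude profiles lacking the 24-h sample from that analysis, and report how many. Use AUC0-8 as a sensitivity analysis, since the 0, 1, 2, 4, 6 and 8 h samples are scheduled in every full profile. AUC0-8 should not lead, because it would discard the 12-h and 24-h samples scheduled for all Part 1 subjects.
- **Day 1:** AUC0-24 for Part 1, AUC0-8 for any comparison that includes the Expanded Cohort, and AUC0-72 for Cohorts 1-4 only.

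Reconcile protocol Sections 5.4.4 and 5.4.5 and the Part 2 schedule (with SAP Table 4) against the synopsis, Section 6.5 and Appendix 3 on Expanded Cohort Day 22/23 PK. Reconcile Section 6.5 with Appendix 3 on Day 2.

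The cost is SAP and protocol wording and a small amount of non-compartmental re-work. The fixed windows need no samples beyond those already scheduled. The downside is the possible loss of a few Expanded Cohort profiles from the AUC0-24 analysis.
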